**Aim 2. To determine the impact of chronic inflammation on responsiveness to acute exercise.**

**Hypothesis 2:** Acute exercise responsiveness is blunted in older adults with chronic inflammation, but restored when inflammation is reduced.

**Approach:** We will combine conventional molecular techniques with tracer-based approaches to evaluate anabolic and metabolic responses to a single bout of exercise in older adults grouped by inflammation status before and after inflammation is reduced by n3-PUFAs. Muscle and blood samples collected before and after a single bout of exercise will be used to measure anabolic and metabolic responsiveness to exercise from mRNA of exercise-responsive genes, activation of signaling proteins in muscle, and whole-body amino acid kinetics. Exercise-stimulated anabolic and metabolic responsiveness will be evaluated again after reducing inflammation in older adults (placebo vs. n3-PUFAs).

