At 0500h infusions of  $^{13}\text{C}_6$  phenylalanine at 1.0 mg/kg FFM/h and  $[^{15}\text{N}]$  tyrosine at 0.5 mg/kg FFM/h will be started after bolus of 1.0 mg/kg FFM  $[^{13}\text{C}_6]$  phenylalanine, 0.5 mg/kg FFM  $[^{15}\text{N}]$  tyrosine, and 0.5 mg/kg FFM  $[^{13}\text{C}_6]$  tyrosine. These are stable (non-radioactive) isotopes. Muscle biopsies from one *v. lateralis* will be obtained at 0830hrs for measuring baseline gene expression, protein expression, and mitochondrial function. Muscle biopsy samples will be collected under local anesthesia (2% lidocaine buffered with sodium bicarbonate) using a modified Bergstrom needle. A single abdominal subcutaneous fat biopsy will be performed at 0830 hrs under local anesthesia using sterile technique. Following the muscle and fat biopsies (~0900hrs), participants will perform a bout of unaccustomed unilateral knee extension exercise using only the leg without prior biopsies. Following a warm-up set, subjects will complete 8 sets of 10 repetitions at 70% of their 1-repetition maximum, determined at least 7 days prior. A second muscle biopsy will be obtained from the exercised leg 3 hours following exercise (~1230hrs).

Following the second biopsy (~1300hr), participants will consume a mixed liquid meal containing 15% protein, 55% carbohydrate, and 30% fat, approximately equal to 35% of resting energy expenditure determined from the REE on the outpatient study day. Arterialized blood samples will be taken from a heated hand vein for glucose, insulin, and c-peptide measurements at intervals over 5 h after the test meal, which will be consumed over 10 min. Blood samples will be collected at 30, 20, and 10 minutes before the meal and at 0, 5, 10, 15, 20, 30, 40, 50, 60, 75, 90, 120, 150, 180, 210, 240, 260, 280, and 300 minutes following the meal. We are collecting and washing red blood cells for storage for future testing. Resting energy expenditure and respiratory quotient will be measured by indirect calorimetry for 30 minutes under postabsorptive conditions (0700hrs) and postprandial (1430hrs). Participants will be given a meal from the hospital kitchen at approximately 1800hr before discharge.

The inpatient and 48 hour study day will be repeated following the 6 month intervention.

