### 48 hours post-exercise biopsy:

Participants will return to the CRTU for an outpatient study visit involving an additional muscle biopsy from the exercised leg 48 hours following the single bout of exercise.

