The main outcome variables for specific aim 2 are: 1) mRNA expression of anabolic and metabolic signaling genes, 2) expression and activation (phosphorylation) of signaling proteins, and 3) whole-body protein turnover. Hypothesis 2a will be addressed using the pre-treatment measurements, including a baseline and 3 post-exercise time points for all individuals. For each outcome, linear random effects models with time point and the inflammation score interaction terms plus a random intercept for each individual will be estimated. The statistical analysis for hypothesis 2b will be similar to specific aim 1, wherein regression models will be estimated for each outcome variable and include an interaction term between assigned treatment arm and the inflammation score. Missing data and loss to follow-up will be handled as described above in aim 1. Power calculations were performed using the preliminary data in which protein synthesis was measured using the same exercise protocol proposed in this aim. We utilized a linear random intercept model with a baseline and 3 post intervention time point and assuming an exchangeable correlation matrix with pairwise correlation of 0.7 within an individual between time points. With  $\sigma = 0.025 \text{ %/hr}$ , a sample size of 30 per inflammation group gives 80% power ( $\alpha=0.05$ ) to detect a  $0.028 \text{ %/hr}$  slope change between inflammation groups in muscle protein synthesis in response to exercise. We believe that this minimal detectable difference is meaningful, realistic, and conservative.

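### Hypothesis 2a is powered on a slope while its model leaves the coding of time open; if time is linear, the 3 h response gets zero or negative weight, and the stated 0.028 %/hr does not follow from its inputs

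*Combined protocol and SAP*

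**What the plan says.** Aim 2 states the hypothesis as "Acute exercise responsiveness is blunted in older adults with chronic inflammation, but restored when inflammation is reduced". Its first half, called 2a in the statistical section, is about how far a single bout of exercise moves the outcomes away from baseline.

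For the analysis, the section Statistical analyses and Power says that "linear random effects models with time point and the inflammation score interaction terms plus a random intercept for each individual will be estimated". It gives no coding for time and names no contrast.

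The power statement in the same paragraph uses a linear random-intercept model with baseline and three later points, exchangeable correlation 0.7 and SD 0.025 %/hr. It reports that "a sample size of 30 per inflammation group gives 80% power" for 0.028 %/hr, described as a "slope change between inflammation groups in muscle protein synthesis in response to exercise".

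In the inpatient study day description, the baseline biopsy is at 0830 h and "A second muscle biopsy will be obtained from the exercised leg 3 hours following exercise". A separate visit adds an "additional muscle biopsy from the exercised leg 48 hours following the single bout of exercise". These are two timed post-exercise biopsies, against the three post-exercise points in the statistical section. Sources of Materials, under Human Subjects, allows two or three biopsies per inpatient visit.

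**The concern.** A blunted acute response is a smaller rise from baseline to a post-exercise sample. A slope is a straight-line trend over all the time points. The two have different null hypotheses, and they differ most when a response peaks early and fades, which is the pattern that a 3 h biopsy is placed to catch. The slope is the only effect that the plan names for hypothesis 2a. An analyst who takes the power statement as the guide to the model could miss real blunting at 3 h, or report a significant difference in the opposite direction. Another analyst, reading the same paragraph as categorical time, would find it. The power figure is also the only justification given for the sample size in Aim 2, so it matters which quantity it describes.

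**Working it through.** **Inputs** (Statistical analyses and Power, Aim 2 paragraph): SD 0.025 %/hr, correlation 0.7, 30 per group, power 80%, alpha 0.05. Two-sided testing is assumed, because the plan does not state the sidedness. The multiplier is 1.960 + 0.842 = 2.802.

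**Step 1. The plan's own figure.** In a balanced random-intercept model, the between-group slope difference has SE = SD × √[(1 − ρ)/Sxx × 2/n]. For four equally spaced points, Sxx = 2.25 + 0.25 + 0.25 + 2.25 = 5.

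- Slope per step: SE = 0.025 × √(0.3/5 × 2/30) = 0.00158. The detectable difference is 2.802 × 0.00158 = 0.0044, or 3 × 0.0044 = 0.0133 over the whole range.
- The same with the SD taken as residual: SE = 0.025 × √(1/5 × 2/30) = 0.00289, giving 0.0081 per step and 0.0243 over the range.
- Change from baseline: contrast SD = 0.025 × √(2 × 0.3) = 0.0194, SE = 0.0194 × √(2/30) = 0.0050, detectable difference 0.0140 %/hr.
- Single time point: SE = 0.025 × √(2/30) = 0.00645, detectable difference 0.0181.

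None of these gives 0.028. Under the stated slope model 0.028 would have more than 99.9% power. Variants that come close need inputs that the plan does not state, such as 15 per group, or alpha divided by 3 with a residual SD and the correlation unused.

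**Step 2. Weight of each sample in a slope.** The weights are (t − mean t)/Sxx.

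- Codes 0, 1, 2: −0.5, 0, +0.5. The 3 h biopsy has no influence.
- Hours 0, 3, 48 (mean 17, Sxx = 289 + 196 + 961 = 1446): −17/1446, −14/1446, +31/1446. A lower 3 h value raises the slope.
- Codes 0 to 3, matching the four points in the statistical section: −0.3, −0.1, +0.1, +0.3. The first post-exercise value again has a negative weight.

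**Step 3. When the sign is wrong.** Let the inflamed group be lower by D at 3 h and by f × D at 48 h. In hours, the slope difference (inflamed minus comparison) is D × (14 − 31f)/1446. It is positive, the wrong direction, when f is below 14/31 = 0.45.

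For D = 0.028 and f = 0, the difference is 0.028 × 14/1446 = 0.000271 per hour. Its SE is 0.025 × √(0.3/1446 × 2/30) = 0.000093, so z = 2.9. With known variance, the chance of a significant wrong-direction result is 83%.

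**Step 4. Illustrative rejection rates.** Simulation of 20,000 replicates, three samples, D = 0.028. The error variance is pooled from the fitted straight line, and the comparison group has no exercise response.

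| Deficit left at 48 h | Slope, codes 0, 1, 2 | Slope, hours | Joint time-by-group test |
|---|---|---|---|
| none | 1% | 67%, wrong direction | about 100% |
| one quarter | 15% | 13%, wrong direction | about 100% |
| one half | 68% | 2% | about 100% |
| all | 100% | 86% | 100% |

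These rates move with assumptions that the documents do not settle. For a deficit at 3 h only, in hours, the wrong-direction rate is 83% with known variance, 67% as tabulated, and about 28% if the comparison group itself rises by 0.05 %/hr at 3 h. For a sustained deficit in hours, the right-direction rate is 94%, 86% and about one half under the same three settings.

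**Step 5. The alternative.** With categorical time, the baseline-to-3 h contrast has 80% power for 0.014 %/hr and more than 99.9% for 0.028. The joint test does worse than the slope in some cases: for a deficit of 0.014 at 48 h only, it rejects 82%, against 89% for the slope in hours and 78% with codes 0, 1, 2.

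**The case against.** The strongest reply is that the plan never commits the analysis to a slope. The analysis sentence speaks of time points and of interaction terms in the plural, which fits a categorical factor at least as well as linear time. On that reading the 3 h contrast is already estimable and well powered. The power wording may simply be loose: 0.028 carries the unit %/hr, the same as the SD, whereas a slope over clock time would need a further per-hour unit. This stands. A reader might infer that hypothesis 2a will be tested by a slope and will return the wrong direction; the documents do not establish that.

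Three further objections carry weight.

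- The statistical section counts three post-exercise points, so calculations on three samples may not match the intended design. A third inpatient biopsy would make up the count, but no time for it is given in the sections available here. The sign problem survives with four equally spaced points.
- No time course is stated, and sustained blunting keeps the right sign.
- The powered outcome, muscle protein synthesis, is not on the list of main Aim 2 outcomes, so the slope wording is not attached directly to mRNA or signalling.

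None of this rescues the power statement. If time is categorical, that statement describes a quantity that is not tested; if time is linear, its figure does not follow from its inputs. Nor does the mismatch show that Aim 2 is underpowered: for the quantities in Step 1, the stated inputs give detectable differences smaller than 0.028.

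**Conclusion.** The point holds in conditional form. The only effect that the plan names for hypothesis 2a is a slope, a slope is a poor measure of an acute response on this sampling schedule, and the analysis text does not exclude it. If time is linear, early blunting is given zero or negative weight. In hours, the sign is wrong whenever the 48 h deficit is below about 45% of the 3 h deficit. If time is categorical, that harm does not arise.

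The weights and the 45% threshold are arithmetic and depend only on the timing of the samples. The rejection rates are illustrative: about 28% to 83% in the wrong direction for one and the same deficit of 0.028 at 3 h only, depending on the comparison group's own response and on how error variance is estimated.

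Under either reading, 0.028 %/hr is not what the stated inputs give (0.0044 per step, 0.0133 over four points, 0.0140 for a change from baseline), and the number of post-exercise points does not match the visible schedule. This should be corrected before analysis, but it does not call the design or the sample size into question.

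**What to change.** In the Aim 2 paragraph of Statistical analyses and Power:

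1. State that exercise time point is a categorical factor.
2. Test hypothesis 2a by the joint time-point-by-inflammation-score interaction, and report the baseline-to-3 h and baseline-to-48 h contrasts by score with confidence intervals.
3. Reconcile the three post-exercise points with the biopsies in the inpatient day, the 48 h visit and Sources of Materials, and give the time of any further sample.
4. Replace the slope in the power statement by the difference in change from baseline at a named time point, and restate the detectable difference: about 0.014 %/hr for two groups of 30 under the stated inputs, with the SD taken as total and a two-sided test.

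The cost is a change of wording and a restated power sentence, with no extra samples or participants. The joint test uses extra degrees of freedom and loses a few points of power if the response is truly linear or confined to the last time point (82% against 89% in the least favourable case simulated).

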## **Human Subjects**

### **1. Risks to the subjects**

**Human Subjects Involvement and Characteristics:** All protocols and all techniques to be used will be approved by the Mayo Clinic Institutional Review Board prior to initiation of any studies. Subject characteristics and exclusion criteria have been clearly specified above. All women of child bearing potential will have a negative pregnancy test within 24 hours of the study and will be advised to refrain from conception for at least two months after the study. No children will be studied. All subjects will be weight stable before enrolling in the study. Our plan is to complete the study on 135 participants.

**Sources of Materials:** Samples of blood, skeletal muscle, and adipose tissue obtained during the study will be used exclusively for research purposes. Data on body composition will be used only for research. No use will be made of pre-existing specimens.

***Muscle tissue:*** Two or three muscle biopsies (~300mg each) will be obtained during each inpatient study visit.

***Blood:*** 1 blood draw will occur during the screening visit (approximately 15ml). Each inpatient study will require 48 blood draws (approx 407mL blood). All specimens will be processed internally and stored in the study team laboratory.

***Adipose tissue:*** One subcutaneous abdominal fat biopsy (2-3g) will be obtained during each inpatient visit.

### **Potential Risks: The following are the potential risks for this study:**

a) Blood will be withdrawn. The total blood withdrawn will not exceed 550mL in a 12-week period. Hemoglobin measured before starting the study will be within safe limits as decided by the investigators. All subjects will refrain from giving blood twelve weeks prior to the study and until twelve weeks after the completion of the study.

b) DEXA will be completed on all subjects for all specific aims. The radiation exposure from this technique is within the safe limits as determined by the Radiation Safety Committee of our institution. Scans are done on the Lunar iDXA, software version 11.4 (General Electric Company, GE Healthcare Technologies, Madison, WI). This can be done with sufficiently low radiation exposure that pregnancy testing is not required.

c) Vascular catheters will be placed. Catheter insertion, intravenous infusion and blood withdrawal are associated with a small risk of phlebitis. This will be minimized by careful attention to sterile technique. If phlebitis occurs, it will be treated conservatively with heat and when appropriate, with antibiotics. In all experiments, “arterialized – venous” blood will be obtained by placing a hand in which a catheter has been inserted in a heated box during the study. The temperature inside the box is maintained at ~55°C. With prolonged exposure to continuous heat, there is a potential risk of local skin irritation or a minor burn. If this occurs, it will be treated appropriately. However we have used this technique for the past 18 years and have had no instances of hot box-related burns or injuries. The potential risks of catheters and hot box use will be discussed with the volunteers prior to obtaining consent for the study.

d) Muscle biopsies will be performed with a percutaneous biopsy needle by the PI or an appropriately-trained member of his study team in accordance with approval from the Research Resources Executive Committee. Local subcutaneous injection of 2% lidocaine buffered with 8.4% sodium bicarbonate will be used for analgesia. A small incision will be made through the skin and fascia. After the biopsy, pressure will be held over the incision until hemostasis is achieved. The incision is closed with sterile strips, gauze and Ace wrap. Risks of this procedure include hematoma, infection, and pain. Hematoma likelihood is minimized by holding pressure after the biopsy to ensure hemostasis, followed by a pressure dressing. Risk of infection is minimized by using sterile surgical techniques. Pain is managed by local analgesia during the procedure and Tylenol following the procedure.

e) Whole-body cardiorespiratory fitness will be evaluated by a graded exercise test on a treadmill. Risks include chest pain, arrhythmias, myocardial infarction, and hyperventilation syndrome. We will monitor these risks by having only trained personnel with CPR training performing the testing. Continuous ECG and blood pressure monitoring will be performed a minimum of every 2 minutes during the test and 5 minutes following the test. Pretest history and physical examination will be performed with emphasis on signs and symptoms of cardiac, vascular or pulmonary disease. Levels of perceived exertion will be asked every 2 minutes. Emergency resuscitation equipment and drugs and telephone to activate code team are in testing room. Attention to exercise test end points will be made.

f) Fat biopsies will be taken from the abdomen. The risks of these procedures include pain, hematomas, bruising, infection, and scaring of the biopsy site. The risk of pain and bruising from adipose tissue biopsies is high, and the volunteers are given this information. We reduce the risk of infection by performing all biopsies under sterile conditions. Nonetheless, each volunteer is told of the signs symptoms of infection and is told to call the study coordinator immediately should any of they occur. A record is kept of all adverse reactions to biopsies. If an increase in the number of adverse reactions relative to historical controls is observed during the course of a particular study a careful assessment of technique and approaches is made. The protocol might then be modified or additional instruction or supervision of the individual performing the biopsies could be undertaken. The subsequent results are then audited to determine how effective the intervention has been.

## **2. Adequacy of Protection against Risks**

**Feasibility, Recruitment and Informed Consent:** Volunteers will be initially recruited from individuals who have previously indicated a desire to participate in research. Volunteers will be recruited from advertisements placed on the Mayo Clinic and appropriate Mayo Health System (MHS) bulletin boards, electronic bulletin boards, in local newspapers and the Mayo Health System Newsletter. Each willing participant will meet one of the investigators who will explain the scientific rationale of the study, the procedures and potential risks involved in the study. The consent form will be approved by Mayo IRB prior to use. Informed written consent from the participant will be obtained by one of the investigators prior to participation. An electronic note will be entered in each participant's medical record regarding the consent and a copy of the consent will be electronically kept with the participant's medical record. A copy of the consent will be given to the subject and the original kept with the investigators records.

**Protection against Risk:** All protocols and all techniques to be used will be approved by the Mayo Clinic Institutional Review Board prior to initiation of any studies. All participants will have the Mayo Clinic paging operator available to them 24 hours a day to contact the investigators for any problems. The Clinical Research Unit also has an on-call physician available 24 hours a day to contact for problems or concerns. The following protection will be taken for the risks identified above:

1. Intravenous risks will be minimized by having experienced CRTU staff place the lines and infusing 0.9% normal saline throughout the study to decrease the risk of phlebitis or occlusion.
2. All infusions will be prepared in the pharmacy or by a trained nurse or doctor to ensure accuracy of all infusion concentrations and rates.
3. The amount of blood drawn is within the amounts acceptable by the institution. There is an institutional electronic tracking system to ensure that a patient is not in more than one study at a time.
4. The Radiation Safety Committee will approve the study for radiation safety of the Lunar iDXA scan.
5. A DSMP will be utilized for patient safety. A DSMB is not necessary for the study. Investigators and the CRTU have had extensive experience in all procedures and aspects of the study. The investigative team will review any participant safety issues as delineated in the DSMP.
6. Subject protection is as listed in the above section. Confidentiality of all medical records is strictly maintained by established procedures. The original study data are kept in the principal investigators' laboratory/office and are entered into a secure computer database password protected under a secure server space behind the Mayo firewall allocated for use by only the study team. All data are reviewed by the principal investigator. All investigators carry pagers. Volunteers have access to the Mayo Clinic paging operator 24 hours a day.
7. Risk for infection from muscle and fat biopsies is minimized by using sterile surgical technique. Participants will be educated on proper post biopsy care to further minimize infection risk.
8. The risks to the subjects are small being primarily those of blood withdrawal, catheter insertions and muscle biopsies.

### **3. Potential Benefits of the Proposed Research to the Subjects and Others**

Muscle health has a tremendous impact on physical function and metabolic health. Although exercise is an effective strategy to enhance muscle and metabolic health, there is emerging evidence that some people exhibit blunted responsiveness to exercise. Chronic systemic inflammation may be a factor that contributes to this so-called exercise resistance. The proposed studies will determine the relationship between systemic inflammation and salient parameters of skeletal muscle function. Such information will help identify effective strategies to manage sarcopenia, diabetes, and other chronic diseases that influence muscle physiology. The risks to the patients are minimal compared to the knowledge gained from the study.

